#### 9.4 Determination of Sample Size

This Study is exploratory and its sample size is not determined by statistical power considerations, but is considered appropriate for an early phase safety trial.

#### 9.5 Interim Analysis

No formal interim analysis for efficacy is planned, as this is a study with careful monitoring of subject safety in an ongoing manner by the principal investigator, Sponsor and independent Data Safety Monitoring Board.

## 9.6 Data Quality Assurance

The following steps will be taken to ensure the accuracy, consistency, completeness, and reliability of the data:

- Investigator meeting
- Routine study site monitoring
- CRF review against source documents
- Data management quality control checks
- Sponsor medical review

The sponsor or designee (e.g., contract research organization (CRO)) will be responsible for the data management of this clinical trial. The responsible party will design and distribute the case report forms (CRFs), and also conduct monitoring of the CRFs. The responsible party will generate queries in the event of incomplete or inconsistent data to be reconciled by the study site.

#### **10 INVESTIGATOR REQUIREMENTS**

#### 10.1 Study Initiation

Before the release of investigational products to the study site, the following documents must be on file with CardioCell LLC or its designee:

- U.S. FDA Form 1572 signed by the Principal Investigator or equivalent for non-U.S. sites if applicable.
  - The names of any sub-investigators must appear on this form. Investigators must also complete all regulatory documentation as required by local and national regulations.
- Current curricula vitae (CV) of the Principal Investigator and all subinvestigators
- subinvestigators
- Complete financial disclosure forms for the Principal Investigator and all subinvestigators
- Written documentation of Institutional Review Board (IRB)/Ethics Committee (EC) approval of the protocol (identified by protocol number or title and date of approval) and Informed Consent Form (identified by protocol number or title and date of approval)
- A copy of the IRB/EC-approved Informed Consent Form
- IRB/EC composition or assurance letter as applicable
- Current laboratory certification of the clinical laboratory performing sample analysis, as well as current references ranges for all laboratory tests (*if applicable*)
- A Clinical Trial Agreement signed and dated by the study site
- Investigator Brochure receipt signed and dated by the Principal Investigator (if applicable)
- A Protocol Acceptance Form signed and dated by the Principal Investigator

## 10.2 Study Completion

The following data and materials are required before a study can be considered complete or terminated:

- All essential documents (e.g., curriculum vitae for the Principal Investigator and subinvestigator, U.S. FDA Form 1572 or equivalent (non-U.S.)
- Copies of protocol amendments, IRB/EC approval/notification, and signed and dated Protocol Amendment Acceptance Form(s) *(if applicable)*
- All data collection and query resolution complete Original, final SAE reports and all supporting documentation (i.e., discharge summaries, laboratory results)
- Original, final Pregnancy Information forms and all supporting documentation (*if applicable*)
- Complete and accurate investigational product accountability records and inventory log
- Laboratory results, clinical data, and all special test results from screening through the end of the study
- A summary of the study prepared by the principal investigator (IRB/EC summary close out letter is acceptable)

#### **10.3 Informed Consent Process**

CardioCell, LLC Informed Consent Form (ICF) will be provided to the hospital site. CardioCell, LLC or its designee must review and approve any proposed deviations from the ICF or any alternate consent forms proposed by the site before IRB/EC submission. Subjects must be re-consented to the most current version of

the ICF during their participation in the study. The final IRB/EC-approved ICF must be provided to CardioCell, LLC or its designee for regulatory purposes.

The ICF must be signed by the subject or the subject's legally authorized representative before his or her participation in the study. The case history for each subject shall document the informed consent process and that written informed consent was obtained prior to participation in the study. A copy of each signed ICF must be provided to the subject or the subject's legally authorized representative. It will be provided in a certified translation of the local language(s).

All signed and dated ICF must remain in each subject's study file and must be available for verification by study monitors at any time.

The ICF will be revised whenever there are changes to procedures outlined in the informed consent or when new information becomes available that may affect the willingness of the subject to participate.

## **10.4** Institutional Review Board or Ethics Committee

This protocol, the ICF, any information to be given to the subject and relevant supporting information must be submitted to the IRB/EC by the Principal Investigator for review and approval before the study is initiated as required by the country regulatory authority. In addition, any subject recruitment materials must be approved by the IRB/ EC.

The Principal Investigator is responsible for providing written summaries of the status of the study to the IRB/EC annually or more frequently in accordance with the regulatory requirements and policies and procedures established by the IRB/EC. Investigators are also responsible for promptly informing the IRB/EC of any protocol changes or amendments and of any unanticipated problems involving risk to human subjects or others. In addition to the requirements to report protocol-defined AEs to the Sponsor, Investigators may be required to promptly report to their respective IRB/EC all unanticipated problems involving risk to human subjects. Some IRB/ECs may want prompt notification of all SAEs, whereas others require notification only about events that are serious, assessed to be related to study stem cell administration, and are unexpected. Investigators may receive written Investigational New Drug (IND) safety reports or other safety-related communications from CardioCell, LLC. Investigators are responsible for ensuring that such reports are reviewed and processed in accordance with regulatory requirements and with the policies and procedures established by their IRB and archived in the site's Study File.

#### 10.5 Study Monitoring Requirements

Site visits will be conducted by an authorized CardioCell, LLC representative to inspect study data, subjects' medical records, and CRFs. The Principal Investigator will permit CardioCell, LLC monitors/representatives and collaborators, the U.S. FDA or other regulatory agencies, Ethics Committees and the respective national or local health authorities to inspect facilities and records relevant to this study, in accordance with GCP and the ICH E6 guidance. If the investigator is notified of an audit pertaining to this study by the U.S. FDA or other applicable regulatory authorities, the Investigator must notify CardioCell, LLC immediately.

The Investigator must provide sufficient space and allocate sufficient time for the monitor to inspect subject source records, CRFs, investigational product accountability records, and regulatory documents.

#### 10.6 Case Report Forms

CRFs will be supplied by CardioCell, LLC or its designee and will be handled in accordance with the instructions. All CRFs will be filled out completely by designated personnel.

## 10.7 Source Data Documentation

Study monitors will perform ongoing source data verification to confirm that critical protocol data (i.e., source data) transcribed on the CRFs by authorized site personnel are accurate, complete, and verifiable from source documents. Source documents are where subject data are recorded and documented for the first time. They include, but are not limited to, hospital records, clinical and office charts, laboratory notes, memoranda, subject diaries or evaluation checklists, pharmacy dispensing records, recorded data from automated **Protocol:** STEM-104-M-CHF 32 19FEB2014

instruments, copies of transcriptions that are certified after verification as being accurate and complete, microfiche, photographic negatives, microfilm or magnetic media, X-rays, subject files, and records kept at the pharmacy, laboratories, and medico-technical departments involved in a clinical trial. Source documents that are required to verify the validity and completeness of data transcribed on the CRFs must never be obliterated or destroyed. To facilitate source data verification, the investigator(s) and institution(s) must provide the sponsor direct access to applicable source documents and reports for trial-related monitoring, sponsor audits, and IRB/EC review. The investigational site must also allow inspection by applicable regulatory authorities.

## 10.8 Use of Computerized Systems

When clinical observations are entered directly into an investigational site's computerized medical record system (i.e., in lieu of original hardcopy records), the electronic record can serve as the source document if the system has been validated in accordance with ICH requirements pertaining to computerized systems used in clinical research. An acceptable computerized data collection system (for clinical research purposes) would be one that (1) allows data entry only by authorized individuals; (2) prevents the deletion or alteration of previously entered data and provides an audit trail for such data changes (e.g., modification of file); (3) protects the database from tampering; and (4) ensures data preservation. If a site's computerized medical record system is not adequately validated for the purposes of clinical research (as opposed to general clinical practice), applicable hardcopy source documents must be maintained to ensure that critical protocol data transcribed on the CRFs can be verified.

#### **10.9** Investigational Product Accountability

All investigational products required for completion of this study will be provided by CardioCell, LLC. The recipient will acknowledge receipt of the drug by returning the appropriate documentation form indicating shipment content and condition. Damaged supplies will be replaced.

Accurate records of all study drug received at, dispensed from, returned to and disposed of by the study site will be recorded.

Investigational product will either be disposed of at the study site according to the study site's institutional standard operating procedure or returned to CardioCell, LLC with the appropriate documentation, as determined by the study site. If the study site chooses to destroy investigational product, the method of destruction must be documented.

CardioCell, LLC must evaluate and approve the study site's drug destruction standard operating procedure prior to the initiation of drug destruction by the study site.

#### 10.10 Disclosure of Data

Subject medical information obtained by this study is confidential, and may only be disclosed to third parties as permitted by the ICF and Authorization Form (or separate authorization to use and disclose personal health information) signed by the subject or unless permitted or required by law.

Medical information may be given to the subject's personal physician or other appropriate medical personnel responsible for the subject's welfare for treatment purposes.

Data generated by this study must be available for inspection upon request by representatives of the applicable regulatory agencies, national and local health authorities, CardioCell, LLC monitors/representatives and collaborators, and the IRB/EC for each study site, if appropriate.

#### **10.11** Retention of Records (for approval enabling studies only)

United States FDA regulations (21 CFR §312.62[c]) and the ICH Guideline for GCP (E6) require that records and documents pertaining to the conduct of this study and the distribution of investigational drug, including CRFs, consent forms, laboratory test results, and medication inventory records, must be retained by the Principal Investigator for 2 years after the last marketing application approval in an ICH region or after at least

2 years have elapsed since formal discontinuation of clinical development of the investigational product. All state and local laws for retention of records also apply.

No records will be disposed of without written approval from CardioCell, LLC. Written notification will be provided to CardioCell, LLC for transfer of any records to another party or moving them to another location.

#### APPENDIX A: SCHEDULE OF ASSESSMENTS

Visit	1	3	4	5	6	7	8	9	Early
Day	Days 1 to 2	Day 7±3	Day 30±7	Day 60±7	Day 90±7	Day 120±10	Day 150 ±7	Day 180±10	Termination
Informed Consent Form	Х								
IV Infusion		Х			X				
Final Formulation Skin Test *		Х			X				
Pregnancy Test ^	Х			~	Х			Х	Х
Troponin, HIV	Х								
Randomization into experimental or control group	Х								
Cardiac MRI	Х				X			Х	Х
Medical History	Х								
Spirometry/DLCO	Х				X			Х	
Full 2D Doppler transthoracic echocardiography with speckle-tracking †	Х				X			Х	Х
SF-36 Health Assessment, Canadian Cardiovascular Society (CCS) angina classification, KCCQ, NYHA	Х		X	X	X	Х	Х	Х	Х
Concomitant medications	Х		X	X	Х	Х	Х	Х	Х
12-lead ECG	Х	X	Х	Х	Х	Х	Х	Х	Х
24 hour Holter ECG recording*	Х		Х	Х	Х	Х	Х	Х	Х
Pulse Oximetry**	X	Х	Х	Х	Х	Х	Х	Х	Х
Vital Signs**	X	Х	Х	Х	Х	Х	Х	Х	Х
6 minute walk test	X		Х	Х	Х	Х	Х	Х	Х
Physical Examination	X	Х	Х	Х	Х	Х	Х	Х	Х
Cardiac Examination	Х	Х	Х	Х	Х	Х	Х	Х	Х
CBC with Diff	X		Х	Х	Х	Х	Х	Х	Х
Serum Chemistry with BUN/Creatinine, LFT	Х	Х	Х	Х	Х	Х	Х	Х	Х
VEGF, FGF, NT-proBNP	X	Х	Х	Х	Х	Х	Х	Х	Х
IgA, IgE, IgG, IgM and Lymphocyte Proliferation Panel		Х		Х	Х	Х	Х	Х	Х
Adverse Events		Х	Х	Х	Х	Х	Х	Х	Х
Cardiac Biomarkers (CK and CK-MB fraction, troponin I)	Х	Х	Х	Х	Х	Х	Х	Х	Х
Composite of all-cause mortality, myocardial infarction, coronary revascularization, and admission for worsening HF and all-cause admissions			X	Х	Х	Х	Х	Х	Х

† Ejection fraction must be ≤ 40%.
 ‡ A coronary angiogram performed during the index MI may be used to determine eligibility.

×Skin Test (Appendix C) to be performed prior to IV infusion

\*24 hour Holter ECG recording must be completed prior to IV infusion.

Collect 5mL of blood into tube for lymphocyte proliferation panel prior to IV infusion. Provide 2mL of serum in another tube of IgA, IgE, IgG and IgM test. Serum is taken from blood in 5mL tube, which is centrifuged for 15 minutes at 3500 RPM.

\*Vital signs taken every 2 hours after infusion and pulse oximetry taken continuously for 2 hours after IV infusion. Vital signs include temperature, blood pressure, heart rate respiratory rate and weight †† A test will be taken prior to IV infusion to establish baseline. Another test will be taken 6 hours ± 30 minutes after infusion. If levels are significantly elevated, two more tests will be taken every 6 hours for the next 12 hours.

Need continuous ECG monitoring during infusion

Patient to go home with Holter monitor to assure no arrhythmias immediately post

^Pregnancy test for women of childbearing potential only.

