#### 4 STUDY DESIGN

#### 4.1 Description of the Study

This is a Phase IIa, single-blind, placebo-controlled, crossover, multi-center, randomized study in subjects with N-IHF. Within 3 ±2 days all study participants who meet the eligibility criteria will receive the treatment.

The study will enroll a minimum of 20 subjects and will consist of 2 cohorts. Enrolled subjects will be randomized at 1:1 into an experimental group (n=10), or a placebo group (n=10). Subjects in the experimental group will receive 1.5 million cells per kg and subjects in the placebo group will receive 1 mL/kg LRS. At 90 days the two groups will change arms and the placebo group will receive 1.5 million cells per kg and the initially treated group will receive a Lactated Ringer's Solution (LRS) at a volume of 1 mL/kg.

After discharge, subjects will have safety evaluations per Appendix A. Adverse events, concomitant medications, and assessments will be recorded at each follow-up visit. Complete examinations will be used to assess disability and functional status at baseline (prior to treatment), and at the visits scheduled at 30, 60, and 90, after the initial administration. The same process will be followed at visits scheduled at 30, 60, and 90 days after the new administration (crossover phase). A baseline magnetic resonance imaging (MRI) with delayed contrast enhancement and T2 imaging, as well as a full 2D and Doppler transthoracic echocardiography with speckle-tracking will be performed at baseline and at specific time points during follow-up. All performed MRIs will be assessed in a blinded core lab.

Subjects will continue all of their regular medications unless contraindicated. Subjects may be administered beta-blockers, ACE inhibitors or angiotensin receptors blockers, mineralocorticoid receptor antagonists, statin agents, or other medications, as tolerated. Protocol: STEM-104-M-CHF 16 19FEB2014

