#### 6.2 IV Administration of aMBMC or Placebo

On the day of infusion, prior to study product administration, a skin test will be administered using 0.1 mL aliquot of the Final Formulation (Appendix C).

An intravenous line will be placed into an appropriate vein on the upper extremity or hand with 0.9% sodium chloride solution running to keep the vein open. The study solution described above will be taken up in an 18-gauge needle into a 60 mL syringe with an eccentric (offset) tip. The needle will be removed and infusion tubing will be attached to the syringe. The syringe with infusion tubing will be placed in a metered dose syringe pump positioned horizontally with the syringe rotated such that the syringe tip is at the lowest position. The product will be infused intravenously into the subject's arm at a constant rate of approximately 2 mL/min. The applicable volume for the target dose will be delivered within  $\pm$  2 mL. Depending on subject's weight, up to three 60 mL syringes of product may be infused. After the entire product volume is delivered, 25 mL of LRS (without cells) will be infused at 2 mL/min to deliver cells from the infusion line for more accurate dosing. Subjects in the placebo group will receive intravenous LRS. Their syringes will be labeled as above to preserve blinding and followed by 25 mL of LRS infusion as above.

If the subject has an adverse reaction during the infusion, the infusion may be interrupted or slowed according to the severity of the reaction. All appropriate treatment will be given to reduce any discomfort and ensure the subject's safety. The infusion may be restarted, if interrupted, if the subject is not considered to be at risk by the Investigator and the subject consents.

All subjects will receive the follow-up tests and evaluations as per Appendix A.

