## 7.3 Follow-up Assessments

## Day 30 (±7) days post-infusion

- Measure and record vital signs
- 12-lead ECG
- Pulse Oximetry
- 24 hour Holter ECG recording or ICD assessment
- Record the composite of all-cause mortality, admission for worsening HF and all-cause admissions, and concomitant medication use
- Physical and cardiac examination
- Clinical labs: serum chemistry including BUN & creatinine, CBC with diff, LFT's, total protein and albumin
- Cardiac biomarkers (CK and CK-MB fraction, troponin I)
- Serum/plasma stored for VEGF, FGF, NT-proBNP, troponin
- Kansas City Cardiomyopathy Questionnaire (KCCQ)
- New York Heart Association (NYHA) Classification
- 6 minute walk test

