## Day 60 (±7) days post infusion)

- Measure and record vital signs
- 12-lead ECG
- Pulse Oximetry
- 24 hour Holter ECG monitoring or ACD assessment
- Record the composite of all-cause mortality, admission for worsening HF and all-cause admissions, and concomitant medication use
- Physical and cardiac examination
- Clinical labs: serum chemistry including BUN & creatinine, CBC with diff, LFT's, total protein and albumin
- Cardiac biomarkers (CK and CK-MB fraction, troponin I)
- Serum/plasma stored for VEGF, FGF, NT-proBNP, troponin
- Draw and store blood samples for IgA, IgE, IgG, IgM and for Lymphocyte Proliferation Panel
- Kansas City Cardiomyopathy Questionnaire (KCCQ)
- New York Heart Association (NYHA) Classification
- Spirometry/DLCO
- 6 minute walk test

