#### 7.4 Early Termination Visit

- Measure and record weight and vital signs
- 12-lead ECG
- Pulse Oximetry
- 24 hour Holter ECG monitoring or ACD assessment
- Record the composite of all-cause mortality admission for worsening HF and all-cause admissions, and concomitant medication use
- Physical and cardiac examination
- Clinical labs: serum chemistry including BUN & creatinine, CBC with diff, LFT's, total protein and albumin
- Serum/plasma stored for VEGF, FGF, NT-proBNP, troponin
- Blood sample for IgA, IgE, IgG, IgM and for Lymphocyte Proliferation Panel
- 6 minute walk test
- Kansas City Cardiomyopathy Questionnaire (KCCQ)
- New York Heart Association (NYHA) Classification
- Cardiac MRI, with delayed contrast enhancement
- Full 2D and Doppler transthoracic echocardiography with speckle-tracking

The same follow-up visits will be performed after the crossover phase.

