#### 9.2 Primary Safety Analysis

All safety outcomes will be summarized in tables and listings presented by experimental group. Continuous measures will be summarized with descriptive statistics (N, mean, SD, median, min, max). Categorical measures will be summarized using counts and percentages. The incidence of adverse events will be presented by toxicity grade, MedDRA system organ class and preferred term, and by relationship of the adverse events to the study treatment and compared using a Fisher's Exact Test. Laboratory and vital signs data will be presented using shift tables and summaries of change from baseline to the maximum post-administration value and compared using analysis of covariance (ANCOVA) models.

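### The immunoglobulin and lymphocyte panel is drawn 30 days after the crossover infusion but not 30 days after the first, so no time-matched unexposed control exists for the 30-day immune reading

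*Combined protocol and SAP*

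**What the plan says.** Appendix A carries a row for "IgA, IgE, IgG, IgM and Lymphocyte Proliferation Panel". It is marked at Days 7, 60, 90, 120, 150 and 180 and at early termination, and is empty at screening and at Day 30.

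The body text agrees for the first period. Section 7.2.2 places the Day 7 draw among the pre-infusion tasks. The Day 30 list in Section 7.3 includes clinical laboratory tests, cardiac biomarkers and "Serum/plasma stored for VEGF, FGF, NT-proBNP, troponin", but nothing from this panel. The Day 60 list adds "Draw and store blood samples for IgA, IgE, IgG, IgM and for Lymphocyte Proliferation Panel", and the Day 90 list repeats that item. An Appendix A footnote says "Collect 5mL of blood into tube for lymphocyte proliferation panel prior to IV infusion", so the Day 90 sample precedes the crossover infusion.

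The body text has no separate lists for the visits after crossover. Section 7.4 ends with "The same follow-up visits will be performed after the crossover phase". Section 6.2, on the other hand, says "All subjects will receive the follow-up tests and evaluations as per Appendix A".

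On the design, Section 4.1 states: "At 90 days the two groups will change arms and the placebo group will receive 1.5 million cells per kg", while the group treated first receives LRS.

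On analysis, Section 7.1 lists the panel among the clinical laboratory assessments. Section 9.2 reports laboratory data by shift tables and by "summaries of change from baseline to the maximum post-administration value", compared by ANCOVA, and names no period. The panel is not among the laboratory tests of the primary safety endpoint in Section 4.2.

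**The concern.** Safety is the primary objective and the product is allogeneic, so an immune response is one of the things the trial should be able to see. The earliest scheduled look after an infusion is at 30 days, and for this panel it exists only after the second infusion. By then every subject receiving LRS has already had cells. The one group that could serve as an unexposed control at that time point, placebo-first subjects at Day 30, is not sampled. A sample that was never drawn cannot be recovered in analysis.

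The blank looks unintended. Among the Appendix A rows with marks at follow-up visits, this is the only one whose Day 30 and Day 120 entries differ, and no reason is given.

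**Working it through.** The plan gives no figure on this point to reproduce, so the check is a count of draws followed by a small calculation.

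**Step 1. Draws per period (Appendix A, with Section 7.3 as cross-check).**

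| Days after infusion | Period 1 | Period 2 |
|---|---|---|
| 30 | Day 30: not drawn | Day 120: drawn |
| 60 | Day 60: drawn | Day 150: drawn |
| 90 | Day 90: drawn, before crossover infusion | Day 180: drawn |
| Post-infusion draws | 2 | 3 |

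**Step 2. Who supplies a 30-day reading.** I take 10 subjects per sequence (Synopsis and Section 4.1) and full follow-up. Sections 5.2 and 6.1 print other group sizes, but the argument does not depend on the number.

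- Cells-first, 30 days after cells (Day 30): 0 of 10.
- Placebo-first, 30 days after LRS (Day 30), unexposed: 0 of 10.
- Placebo-first, 30 days after cells (Day 120): 10 of 10.
- Cells-first, 30 days after LRS (Day 120): 10 of 10, all given cells about 90 + 30 = 120 days earlier.

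Half of the treated subjects therefore have no 30-day post-cell reading, and there is no unexposed 30-day LRS reading. Placebo-first subjects are sampled unexposed at Days 7, 60 and 90. The cells-first group's only unexposed reading is its Day 7 baseline.

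**Step 3. Effect on a maximum, if it is taken per period.** For exchangeable normal readings with SD 1 and within-subject correlation ρ, and no treatment effect:

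- E(max of 2) = (1/√π)·√(1−ρ), which is 0.564 at ρ = 0.
- E(max of 3) = (1.5/√π)·√(1−ρ), which is 0.846 at ρ = 0.
- Gap = (0.5/√π)·√(1−ρ).

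| ρ (assumed) | 0 | 0.5 | 0.7 | 0.8 | 0.9 |
|---|---|---|---|---|---|
| Gap, SD | 0.28 | 0.20 | 0.15 | 0.13 | 0.09 |

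A simulation with 1,000,000 replicates agreed with the closed form to within 0.001 SD. The documents give no ρ.

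**Step 4. Does the gap reach the product comparison?** Draws after cells: 10×2 + 10×3 = 50. Draws after LRS: 10×2 + 10×3 = 50. With full completion the pooled comparison is balanced. With unequal dropout, the bias is the gap times the difference in the share of maxima that come from period 2. As an illustration, suppose 2 of the 10 cells-first subjects leave before Day 120 and no one else does: 0.28 × (10/20 − 8/18) = 0.28 × 0.056 = 0.016 SD at ρ = 0.

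**Step 5. The two readings of the schedule.** If Appendix A governs, draws are 2 against 3. If Section 7.4 means that each visit's test list is repeated, Day 120 has no draw, so draws are 2 against 2 and there is no 30-day reading at all. Neither reading gives an unexposed 30-day control.

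**The case against.** Several objections carry weight.

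- **A reader might infer that there is no unexposed control for the panel at all.** The documents do not support that. Days 60 and 90 give a concurrent, randomised, unexposed comparison, and each placebo-first subject's Day 120 value can be set against that subject's own earlier values. What is missing is only the time-matched 30-day control. The within-subject comparison is also mixed up with any change over time.
- **Prior exposure in period 2 comes with the crossover and affects every endpoint.** True. But every other test scheduled 30 days after the second infusion is also scheduled at Day 30, and so has an unexposed 30-day control. This panel does not.
- **A reader might infer that the laboratory maximum is biased between products.** That goes too far. Section 9.2 does not say that the maximum is per period, no comparison between periods is planned, the draws balance at 50 against 50, and a detailed SAP is still to be written. Applying Section 9.2 to this panel is itself an inference. It is a reasonable one, since Section 7.1 lists the panel with the clinical laboratory tests, although the visit lists only say that samples are drawn and stored.
- **A reader might infer a flat contradiction between Section 7.4 and Appendix A.** Section 7.4 speaks of the same visits, not of identical tests, and Section 6.2 and other passages defer to Appendix A. The conflict is possible, not certain.

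The schedule asymmetry itself survives all of these. It is not an extraction artefact, because the Day 30 list in Section 7.3 agrees with the blank cell.

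**Conclusion.** The schedule leaves a real but small gap. Under Appendix A, cells-first subjects have no immune reading 30 days after cells, and the 30-day LRS readings all come from subjects already exposed to cells. Unexposed comparison remains possible at Days 60 and 90. The counts assume 10 subjects per sequence and full follow-up. They are ceilings for those numbers, since a positive skin test, repeated before the crossover infusion, disqualifies a subject (Appendix C).

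The effect on the maximum is secondary and conditional. It arises only if the maximum is per period, and is then 0.28 SD for independent draws or 0.13 to 0.20 SD at an assumed correlation of 0.8 to 0.5. It balances between products with full completion and biases that comparison only under unequal dropout, by little in the case worked above.

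The point is minor: the panel is a supporting safety measure outside the primary laboratory list. It is still worth correcting, because the correction is cheap and the missing samples cannot be obtained later.

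**What to change.** Mark the panel at Day 30 in Appendix A and add it to the Day 30 list in Section 7.3. Both periods then have draws at 30, 60 and 90 days after infusion. This supplies the unexposed 30-day control, gives the cells-first group a 30-day post-cell reading, makes the draw counts 3 against 3 so that the gap in the maximum is zero, and agrees with Section 7.4 on either reading.

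The cost is one more tube and one more immunoglobulin and lymphocyte proliferation assay per subject (20 of each for 20 subjects), at a visit that already draws blood. The change helps only subjects who have not yet passed Day 30.

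In the SAP, add a sentence saying whether the Section 9.2 maximum is taken within each period and from which baseline. Restricting the maximum to the 60- and 90-day draws would equalise the counts without new samples, but it would not supply the missing control and so does not replace the Day 30 draw.
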